10.4 Study Restrictions

10.4.1 Prohibitions and Concomitant Therapy

Consumption of foods and beverages containing the following substances will be prohibited as indicated:

- Xanthines/Caffeine: 24 hours before each dose and throughout the period of sample collection;
- Alcohol: 48 hours before each dose and throughout the period of PK sample collection;
- Grapefruit/Seville orange: 48 hours before the first dose and throughout the study.

Concomitant therapies will be prohibited as listed in the exclusion criteria in [Section 10.3.2](#). During the study, acetaminophen (up to 2 g per 24 hours) may be administered at the discretion of the investigator or designee. Acceptable birth control methods as described in [Section 10.3.1](#) and hormone replacement therapy will be allowed.

If deviations occur, the investigator or designee will decide on a case-by-case basis whether the subject may continue participation in the study based on the time the study drug was administered and its pharmacology.

All medications taken by subjects during the study will be recorded.

10.4.2 Meals

Water (except water provided with each dosing) will be restricted 1 hour prior to and 1 hour after each study drug administration, but will be allowed ad libitum at all other times. Other fluids may be given as part of meals and snacks but will be restricted at all other times throughout the confinement period.

Subjects will fast overnight for at least 10 hours prior to each study drug administration and will continue to fast for 4 hours postdose.

Standard meals will be provided at approximately 4 and 9 hours postdose, and at appropriate times thereafter. Snacks will be provided at appropriate times. When confined in the CRU, subjects will be required to fast from all food and drink except water between meals and snacks.

Each meal and/or snacks served at the CRU will be standardized and will be similar in caloric content and composition and will be taken at approximately the same time in each period/day.

10.4.3 Activity

Subjects will remain ambulatory or seated upright for the first 4 hours following study drug administration, except when they are supine or semi-reclined for study procedures.

However, should AEs occur at any time, subjects may be placed in an appropriate position or will be permitted to lie down on their right side.

Subjects will be instructed to refrain from strenuous physical activity which could cause muscle aches or injury, including contact sports at any time from screening until completion of the study.

10.5 Treatments

10.5.1 Treatments Administered

The test product (for Treatment A) will be supplied as 95 mg MMF delayed-release capsules (Banner Life Sciences).

The reference product (for Treatment B) will be supplied as Tecfidera® 240 mg DMF delayed-release capsules (Biogen, Inc.).

All study drugs will be administered with approximately 240 mL of water following an overnight (at least 10 hours) fast.

Subjects will be instructed not to crush, split, or chew the study drugs.

Treatments A and B are described as follows:

Treatment A (Test): a single oral dose administration of 190 mg MMF (2 x 95 mg delayed-release capsules) at Hour 0 on Day 1.

Treatment B (Reference): a single oral dose administration of Tecfidera® 240 mg DMF (1 x 240 mg delayed-release capsule) at Hour 0 on Day 1.

The pharmacy at the CRU will provide each dose in individual unit dose containers for each subject and for each study period, as per the randomization scheme.

The exact clock time of dosing will be recorded.

10.5.2 Method of Assigning Subjects to Treatment Groups

Each subject will be assigned a unique identification number upon screening. Subjects who complete the study screening assessments and meet all the eligibility criteria will be assigned a unique randomization identification number prior to the first dose, different from the screening number, and will receive the corresponding product, per a randomization scheme generated at Celerion.

Subjects will receive each treatment on one occasion. The sequences to be used in the randomization will be AB and BA.

Space constraints at the CRU may require subjects to be divided into 2 dosing groups of approximately equal size for dosing, as needed. Within each dosing group, subjects will be randomized to receive the test and reference products in a crossover fashion based on a randomization schedule.

Discontinued subjects will not be replaced.

10.5.3 Blinding

This is an open-label study.

10.5.4 Treatment Compliance

A qualified designee will be responsible for monitoring the administration of the timed oral doses. A mouth check will be performed by the qualified designee to ensure that the subjects have swallowed the study drug in whole without chewing. Once a subject has finished the dosing water, the qualified designee will use a flashlight and a tongue depressor to check the subject's mouth. Subjects' hands will also be verified to ensure that the study drug was ingested.

11 STUDY PROCEDURES

The Study Events Flow Chart ([Section 6](#)) summarizes the clinical procedures to be performed at each visit. Individual clinical procedures are described in detail below. Additional evaluations/testing may be deemed necessary by the PI or designee and/or the Sponsor for reasons related to subject safety.

For this study, the blood collection for PK assessment of MMF is the critical parameter event and blood samples need to be collected as close to the exact time point as possible. However, time deviation from scheduled sampling time will not be considered as protocol deviation, as long as the actual clock time of each sample collection is documented in the CRF. All other procedures should be completed as close to the prescribed/scheduled time as possible, but can be performed prior or after the prescribed/scheduled time. The actual date and clock time for all procedures are to be documented in the CRFs.

Any nonscheduled procedures required for urgent evaluation of safety concerns take precedence over all routine scheduled procedures.

11.1 Screening

Within 21 days prior to the first dose, medical history and demographic data, including name, sex, age, race, ethnicity, body weight (kg), height (cm), BMI (kg/m²) and history of tobacco use will be reported. Each subject will have a physical examination, vital sign measurements (heart rate, blood pressure, and temperature), 12-lead ECG, and the laboratory tests of hematological, hepatic and renal function and additional tests as noted in [Section 11.2.4](#).

11.2 Safety Assessments

11.2.1 Physical Examination

A full physical examination (PE) will be performed at screening as per Study Events Flow Chart ([Section 6](#)). Brief PE will be performed on Day -1 of each dose period and symptom-driven PE may be performed at other times, if deemed necessary by the PI or designee.

11.2.2 Vital Signs

Single measurements of body temperature, blood pressure and heart rate, will be measured as outlined in the Study Events Flow Chart ([Section 6](#)). Additional vital signs may be taken at any other times, if deemed necessary.

Vital signs measurements will be performed with subjects in a seated position, except when they are supine or semi-reclined because of study procedures and/or AEs (e.g. nausea, dizziness) or if deemed necessary by the PI or designee.

Blood pressure and heart rate will be measured approximately 2 hours prior to Day 1 dosing of each period for the predose time point. When scheduled postdose, vital signs will be performed within approximately 10 minutes of the scheduled time point.

11.2.3 ECG Monitoring

Single 12-lead ECGs will be performed as outlined in the Study Events Flow Chart ([Section 6](#)). Additional ECGs may be taken at any other times, if deemed necessary by the PI or designee.

ECGs will be performed with subjects in a supine position. All ECG tracings will be reviewed by the PI or designee.

ECGs will be measured approximately 2 hours prior to Day 1 dosing of Period 1.

11.2.4 Clinical Laboratory Tests

All tests listed below will be performed as per Study Events Flow Chart ([Section 6](#)). In addition, laboratory safety tests may be performed at various unscheduled time points, if deemed necessary by the PI or designee.

Hematology

- Hemoglobin
- Hematocrit
- Total and differential leukocyte count
- Red blood cell count
- Platelet count

Urinalysis

- pH
- Specific gravity
- Protein***
- Glucose
- Ketones
- Bilirubin
- Blood***
- Nitrite***
- Urobilinogen
- Leukocyte esterase***

Serum Chemistry*

- Blood Urea Nitrogen
- Bilirubin (total and direct)
- Alkaline phosphatase
- Aspartate aminotransferase
- Alanine aminotransferase
- Albumin
- Sodium
- Potassium
- Chloride
- Glucose (fasting)
- Creatinine**

Additional Tests

- HIV test
- HBsAg
- HCV
- Urine drug screen
 - Opiates
 - Opioids
 - Amphetamines
 - Barbiturates
 - Benzodiazepines
 - Cocaine
 - Cannabinoids
- Urine alcohol screen
- Serum pregnancy test (for females only)
- FSH (for postmenopausal females only)
- Urine cotinine

* Subjects are reminded to fast for at least 8 hours prior to the blood draw for fasting clinical laboratory evaluation.

** At screening, creatinine clearance will be calculated using the Cockcroft-Gault formula.

*** If urinalysis is positive for protein, blood, nitrite and/or leukocyte esterase, a microscopic examination (for red blood cells, white blood cells, bacteria, casts, and epithelial cells) will be performed.

11.2.5 Adverse Events

11.2.5.1 Adverse Event Definition

An AE means any untoward medical occurrence associated with the use of a drug in humans, whether or not considered drug related.

A suspected adverse reaction means any AE for which there is a reasonable possibility that the drug caused the AE. Reasonable possibility means there is evidence to suggest a causal relationship between the drug and the AE.

An AE can therefore be any unfavorable and unintended sign (including an abnormal laboratory finding), symptom, or disease temporally associated with the use of a medicinal (investigational) product, whether or not related to the medicinal (investigational) product.

11.2.5.2 Monitoring

Subjects will be monitored throughout confinement for adverse reactions to the study formulations and/or procedures. Prior to release, subjects will be asked how they are feeling. At the beginning of the second period subjects will be queried with an open-ended question such as: 'How have you been feeling since your last visit?'

AEs (whether serious or non-serious) and clinically significant abnormal laboratory test value(s) will be evaluated by the PI or designee and treated and/or followed up until the symptoms or value(s) return to normal, or acceptable levels, as judged by the PI or designee.

Treatment of serious adverse events (SAEs) will be performed by a physician, either at Celerion or at a nearby hospital emergency room. Where appropriate, medical test(s) and/or examination(s), will be performed to document resolution of event(s). Outcome may be classified as resolved, improved, unchanged, worse, fatal, or unknown (lost to follow-up).

11.2.5.3 Reporting

All AEs that occurred during this clinical study will be recorded. The PI or designee will review each event and assess its relationship to drug treatment (likely, probably, possibly, unlikely or unrelated). Each sign or symptom reported will be graded on a 3-point severity scale (mild, moderate, or severe), and the date of onset, time of onset, and outcome of each event will be noted.

The following definitions will be used for rating the severity of AEs:

- | | |
|----------|---|
| Mild | The AE is easily tolerated and does not interfere with daily activity. |
| Moderate | The AE interferes with daily activity, but the subject is still able to function. Medical intervention may be considered. |
| Severe | The AE is incapacitating and requires medical intervention. |

11.2.5.4 Serious Adverse Event

If any AEs are serious, as defined by the Food and Drug Administration (FDA) Code of Federal Regulations (CFR), Chapter 21, special procedures will be followed. All SAEs will be reported to the Sponsor via fax or e-mail within one working day of becoming aware of the event, whether or not the serious events are deemed drug-related. All serious event reporting will adhere to 21 CFR 312.32 for Investigational New Drugs (IND) and to the Guidance for Industry and Investigators: Safety Reporting Requirements for INDs and BA/BE, dated December 2012. The institutional review board (IRB) will be notified of the Alert Reports as per FDA regulations.

A SAE is any AE or suspected adverse reaction that in the view of either the PI (or designee) or Sponsor, results in any of the following outcomes: Death, a life-threatening adverse event, inpatient hospitalization or prolongation of existing hospitalization, a persistent or significant incapacity or substantial disruption of the ability to conduct normal life functions, or a congenital anomaly/birth defect. Important medical events that may not result in death, be life-threatening, or require hospitalization may be considered serious when, based upon appropriate medical judgment, they may jeopardize the patient or subject and may require medical or surgical intervention to prevent one of the outcomes listed in the above definition. Examples of such medical events include allergic bronchospasm requiring intensive treatment in an emergency room or at home, blood dyscrasias or convulsions that do not result in inpatient hospitalization, or the development of drug dependency or drug abuse.

Life-threatening is defined as an AE or suspected adverse reaction that in the view of the PI (or designee) or Sponsor, its occurrence places the patient or subject at immediate risk of death. It does not include an adverse event or suspected adverse reaction that, had it occurred in a more severe form, might have caused death.

Unexpected is defined as an AE or suspected adverse reaction that is not listed in the IB or is not listed at the specificity or severity that has been observed; or is not consistent with the risk information described in the general investigational plan or elsewhere in the current application, as amended.

If a SAE occurs to a subject on this study, contact the Sponsor personnel listed in [Section 3](#).

11.3 Pharmacokinetic Assessments

11.3.1 Blood Sampling and Processing

For all subjects, blood samples for the determination of MMF will be collected in prechilled blood collection tubes containing sodium fluoride/potassium oxalate as the stabilizer and anticoagulant, respectively at scheduled time points as delineated in the Study Events Flow Chart ([Section 6](#)) by direct venipuncture using a disposable sterile needle at each time of collection.

Blood collection tubes will be placed in an ice bath at least 5 minutes prior to blood collection. Immediately upon blood collection, the collection tubes will be gently inverted

8-10 times to allow mixing with the anticoagulant and the stabilizer, and will be cooled in an ice bath and centrifuged (approximately at 2056 x gravity for 7 minutes) under refrigeration at a temperature of approximately 4°C as soon as possible and no later than 60 minutes upon collection. Plasma samples will be divided into 4 aliquots and stored in suitably labeled polypropylene tubes which are prechilled and contain pre-aliquoted an appropriate volume (100 µL per 1 mL of plasma) of the 10% (v/v) phosphoric acid solution in each tube as a stabilizer. The storage tubes will be labeled, at a minimum, with Sponsor company, protocol number, subject number, sample matrix, study period, study day, scheduled sample time and tube number (eg., #1, #2, #3, #4). Tubes will be stored in an upright position in a non-self-defrosting freezer with the temperature maintained at approximately -70°C or lower until shipment to the designated bioanalytical laboratory where samples will be stored at approximately -70°C or lower. Samples should be placed into the freezer within 90 minutes of blood collection.

At the end of the study, the first aliquot (Aliquot #1) of each plasma sample will be shipped together to the Sponsor's designated bioanalytical laboratory; while the second aliquot (Aliquot #2) will be sent after receipt in good condition of the previous shipment. The other aliquots of each sample will be retained at the CRU until further instruction for shipment.

Additional instruction for blood sampling, collection, processing, and sample shipment will be provided separately.

11.3.2 Analytical Method

Samples will be analyzed for plasma MMF using validated bioanalytical methods. Samples from subjects to be assayed are specified in [Section 12.2.2](#).

11.4 Blood Volume Drawn for Study Assessments

Table 1: Blood Volume during the Study

Sample Type	Number of Time Points	Approximate Volume per Time Point * (mL)	Approximate Sample Volume Over Course of Study (mL)
Screening laboratory safety tests (including hematology, serum chemistry, and serology), FSH (for postmenopausal female subjects only) and serum pregnancy (for female subjects only).	1	12.5	12.5
On-study hematology and serum chemistry (this includes serum pregnancy for female subjects only when scheduled at the same time)	2	12.5	25
Blood for MMF	44	10	440
Total Blood Volume (mL)→			477.5 **

* Represents the largest collection tube that may be used for this (a smaller tube may be used).

** If additional safety or PK analysis is necessary or if larger collection tubes are required to obtain sufficient plasma/serum for analysis, additional blood may be obtained (up to a maximum of 90 mL).

12 DATA ANALYSIS

Data will be handled and processed according to Celerion Standard Operating Procedures, which are written based on the principles of GCP.

12.1 Pharmacokinetic Parameters

PK analysis of plasma concentration vs. time data of MMF will be performed using noncompartmental methods with the following parameters calculated as appropriate or data permitting:

AUC _{0-t} :	The area under the concentration-time curve, from time 0 (dosing time) to the last time point (t _{last}) with measurable drug concentration, as calculated by the linear trapezoidal method.
AUC _{0-inf} :	The area under the concentration-time curve from time 0 (dosing time) extrapolated to infinity. AUC _{0-inf} is calculated as the sum of AUC _{0-t} plus the ratio of the last measurable drug concentration to the apparent terminal first-order decay rate constant.
AUC%extrap:	Percent of AUC _{0-inf} extrapolated from the last time point with measurable drug concentration to infinity calculated as $(1 - AUC_{0-t}/AUC_{0-inf}) * 100$.
C _{max} :	Maximum observed drug concentration.
t _{max} :	Time to reach C _{max} . If the maximum value occurs at more than one time point, t _{max} is defined as the first time point with this value.
Kel:	Apparent terminal first-order decay rate constant calculated from a semi-log plot of the plasma concentration-time curve. The parameter will be calculated by linear least-squares regression analysis using at least 3 appropriate time points in the terminal log-linear phase.
t _{1/2} :	Apparent plasma half-life which will be calculated as $0.693/Kel$.

No value for Kel, AUC_{0-inf}, AUC%extrap, or t_{1/2} will be reported for cases that do not exhibit an apparent terminal log-linear phase in the concentration-time profile. No PK parameters will be calculated for subjects with 3 or fewer consecutive time points with detectable concentrations throughout the collection period.

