- m: Venous blood samples (10 mL each) will be collected at immediately (within 15 minutes) prior to dosing, and then at 0.5, 1, 1.5, 2, 2.5, 3, 3.5, 4, 4.5, 5, 5.5, 6, 6.5, 7, 7.5, 8, 9, 10, 11, 12, and 24 hours postdose.
- n: To be performed at the scheduled time or prior to early termination from the study.

Abbreviations: ♀ = Females, AE = Adverse event, BP = Blood pressure, C-I = Check-in, CRU = Clinical research unit, FSH = Follicle-stimulating hormone, FU = Follow-up, HIV = Human immunodeficiency virus, HR = Heart rate, PI = Principal Investigator, PK = Pharmacokinetic, T = Temperature.

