8 BACKGROUND AND RATIONALE

8.1 Background

8.1.1 Tecfidera® (Dimethyl Fumarate)

Tecfidera® is indicated for the treatment of patients with relapsing forms of multiple sclerosis (MS). The mechanism by which DMF exerts its therapeutic effect in MS is unknown. After oral administration of Tecfidera®, DMF undergoes rapid presystemic hydrolysis by esterases, ubiquitous to the gastrointestinal tract, blood, and tissues, and is converted to its active metabolite, MMF, before it reaches the systemic circulation. Dimethyl fumarate is not quantifiable in plasma following oral administration of Tecfidera®.

Further metabolism of MMF occurs through the tricarboxylic acid cycle, with no involvement of the cytochrome P450 (CYP) system. Monomethyl fumarate, fumaric and citric acids, and glucose are the major metabolites in plasma.

Exhalation of CO₂ is the primary route of elimination, accounting for approximately 60% of the Tecfidera® dose. Renal and fecal elimination are minor routes of elimination, accounting for 16% and 1% of the dose respectively. Trace amounts of unchanged MMF were present in urine.

The terminal half-life ($t_{1/2}$) of MMF is approximately 1 hour and no circulating MMF is present at 24 hours in the majority of individuals. Accumulation of MMF does not occur with multiple doses of Tecfidera®.

No potential drug interactions with DMF or MMF were identified in *in vitro* CYP inhibition and induction studies, or in P-glycoprotein studies. Single doses of interferon beta-1a or glatiramer acetate did not alter the PK of MMF. Aspirin, when administered approximately 30 minutes before Tecfidera®, did not alter the PK of MMF.

DMF and the metabolite, MMF, have been shown to activate the nuclear factor (erythroid-derived 2)-like 2 (Nrf2) pathway *in vitro* and *in vivo* in animals and humans. The Nrf2 pathway is involved in the cellular response to oxidative stress. Monomethyl fumarate has been identified as a nicotinic acid receptor agonist *in vitro*.

The most common adverse reactions (incidence $\geq 10\%$ and $\geq 2\%$ more than placebo) for Tecfidera® were flushing, abdominal pain, diarrhea, and nausea. The incidence of flushing may be reduced by administration of Tecfidera® with food. Alternatively, administration of non-enteric coated aspirin (up to a dose of 325 mg) 30 minutes prior to Tecfidera® dosing may reduce the incidence or severity of flushing.

Refer to the approved US product label for detailed background information on Tecfidera®.¹

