9.2 Study Endpoints

Pharmacokinetics:

The primary endpoints for BE assessment will be comparison of AUC_{0-inf} and C_{max} of MMF between treatments. In addition, AUC_{0-t} will be compared between treatments.

Additional PK parameters AUC% extrapol, t_{max}, K_{el}, and t_{1/2} of MMF will be computed for information.

Safety:

Safety endpoints will include vital signs, clinical laboratory tests, and AEs.

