10.3.3 Early Termination of Subjects from the Study

Subjects are free to withdraw from the study at any time for any reason.

In addition, subjects may be withdrawn from the study by the investigator or designee for the following reasons:

- AEs.
- Difficulties in blood collection.

A subject may be withdrawn by the investigator (or designee) or the Sponsor if enrollment into the study is inappropriate, the study plan is violated, or for administrative and/or other safety reasons.

If a subject vomits within 5 hours after dosing, i.e., a period equal to two times the median t_{max} of MMF after administration of the reference product, he/she may be withdrawn from the study.

The clinical report will include reasons for subject withdrawals as well as details relevant to the subject's withdrawal.

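### With no sample between 12 and 24 h, the linear trapezoidal rule can overstate AUC0-t, and hence AUC0-inf, for late-peaking or slowly eliminated profiles still measurable at 24 h

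*Combined protocol and SAP*

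**What the plan says.** Section 12.1 defines AUC0-t as running to the last time point "with measurable drug concentration, as calculated by the linear trapezoidal method". AUC0-inf is AUC0-t "plus the ratio of the last measurable drug concentration to the apparent terminal first-order decay rate constant", so any error in AUC0-t passes into it.

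The late part of the sampling schedule (Section 6, footnote m) is "7.5, 8, 9, 10, 11, 12, and 24 hours postdose": hourly from 8 to 12 h, then one sample 12 h later.

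Section 8.1.1, which describes the reference product, says the half-life "of MMF is approximately 1 hour and no circulating MMF is present at 24 hours in the majority of individuals". Section 10.3.3 sets its vomiting window at 5 h and describes it as twice the median reference tmax, which implies a median of 2.5 h.

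Sections 9.2 and 12.2.4 make AUC0-inf and Cmax the two decision parameters, each with a 90% CI to lie within 80.00 to 125.00%. Section 12.2 leaves detail to a SAP that may modify the protocol. The supplied text contains no SAP section, no logarithmic rule for the declining phase, and no rule for an isolated measurable value at 24 h.

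**The concern.** After the peak, concentrations fall roughly exponentially, and a straight line between two points on a convex curve lies above it. Over half-hour or hourly intervals the difference is small. Over 12 h it need not be.

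The error appears only when the 24 h sample is measurable. Otherwise AUC0-t stops at or before 12 h and the tail is extrapolated exponentially. It therefore falls selectively on profiles that peak late or decline slowly. Two delayed-release products may differ in how often they give such profiles. If they do, the AUC0-inf ratio shifts for a reason unrelated to exposure. If a subject has such a profile in one period only, the spurious within-subject difference adds residual variance and widens the 90% CI.

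**Working it through.** **The plan's own figure.** The documents give no figure for AUC error, but the sample size fixes the n used below. Section 12.2.1 doses 50 subjects, including 6 for dropout, so 44 are evaluable. With CV 24%, the within-subject SD on the log scale is sqrt(ln(1 + 0.24²)) = 0.237. Two one-sided tests at 5% with n = 44 give power 95.6% at a true ratio of 0.95 and 96.0% at 1.05. The stated 95% reproduces.

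**The 12 to 24 h segment.** The linear area is 6 × (C12 + C24). The area under an exponential decline is (C12 − C24)/k, with k = ln 2 / half-life. Per unit of C12:

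| Half-life | C24/C12 | Linear | Exponential | Ratio |
|---|---|---|---|---|
| 1 h | 1/4096 | 6.00 | 1.44 | 4.16 |
| 2 h | 1/64 | 6.09 | 2.84 | 2.15 |
| 3 h | 1/16 | 6.38 | 4.06 | 1.57 |
| 4 h | 1/8 | 6.75 | 5.05 | 1.34 |

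**Whole profiles.** The effect on total AUC depends on C12. The check used one-compartment profiles with a lag, C(t) proportional to e^(−k(t−lag)) − e^(−ka(t−lag)), on the protocol's 22-point grid. It took AUC0-inf = AUC0-t + Clast/k, with k at its true value. Three inputs are assumptions, not in the documents: ka = 2/h, a lower limit of quantification (LLOQ) between Cmax/100 and Cmax/1000, and the half-life and tmax values tried.

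Worked case, half-life 2 h and tmax 8 h:
- C12 = 0.302 Cmax, and C24 = 0.0047 Cmax (about 1/212).
- Excess over 12 to 24 h = (6.094 − 2.840) × 0.302 = 0.98 Cmax·h.
- The peak comes 1.06 h after the lag, so true AUC = (1/0.347) / e^(−0.347 × 1.06) = 4.17 Cmax·h.
- Excess = 0.98/4.17 = 23.6%. Discretisation error before 12 h is −0.5%, so the total error is +23.1%.

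Error in AUC0-inf against the exact value:

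| Half-life | tmax | C24/Cmax | Linear | Linear-up/log-down |
|---|---|---|---|---|
| 1 h | 2.5 h | about 1/1,900,000 (not measurable) | +1.0% | +0.5% |
| 1 h | 8 h | about 1/43,000 (not measurable) | +0.9% | −0.8% |
| 2 h | 4 h | 1/847 | +5.6% | −0.5% |
| 2 h | 8 h | 1/212 | +23.1% | −1.0% |
| 3 h | 2.5 h | 1/127 | +5.6% | +0.4% |
| 3 h | 5 h | 1/71 | +9.6% | +0.4% |
| 3 h | 8 h | 1/36 | +18.5% | +0.2% |
| 4 h | 2.5 h | 1/38 | +5.1% | +0.1% |
| 4 h | 8 h | 1/15 | +12.9% | 0.0% |
| 1.5 h | 10 h | 1/496 | +52.2% | −7.0% |
| 2 h | 10 h | 1/106 | +43.5% | −3.6% |
| 4 h | 10 h | 1/10 | +19.1% | +1.1% |

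For half-lives of 2 to 4 h and tmax up to 8 h, the linear rule overstates by about 5 to 23% wherever the 24 h sample is measurable, and linear-up/log-down stays within about 1%. At tmax 10 h the linear error is about 20 to 50%. There the log rule is also less exact (up to 7% low), because hourly sampling catches the rise poorly.

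**Effect on the ratio.** If m of 44 Test profiles are overstated by a factor f and their Reference profiles are not, the geometric mean ratio moves by f^(m/44) − 1:
- m = 1: f = 1.05 gives 0.1%, f = 1.25 gives 0.5%, f = 1.50 gives 0.9%.
- m = 3: f = 1.25 gives 1.5%, f = 1.50 gives 2.8%.

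At a true ratio of 1.05, shifts of 0.5 to 0.9% lower power from 96.0% to 95.1 to 94.3%. Shifts of 1.5 to 2.8% lower it to 92.8 to 88.8%.

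**The case against.** The strongest objection is that the condition may seldom arise. At the documented half-life of about 1 h, C24/Cmax is below 1/10,000 for every tmax up to 10 h, so the 24 h sample would not be measurable under the assumed LLOQ range. That stands. It also rules out a tempting inference: that the gap spans about 12 half-lives, so the segment is overstated fourfold in any profile measurable at 24 h. A 1 h half-life with a measurable 24 h sample needs C12 of at least 4096 times the LLOQ. Profiles that do reach 24 h will mostly decline more slowly, and their segment ratio is nearer 1.3 to 2.2.

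Nor is the error always material. If C12 is about 1% of Cmax and C24 is just measurable because of a separate slow tail, the excess is only 0.1 to 1.2% of AUC (taking AUC as 2 to 3.5 Cmax·h and LLOQ as Cmax/200 to Cmax/2000).

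The rule is prespecified and common to both products, so errors shared by a subject's two periods largely cancel. Nothing shows that Test gives more late profiles than Reference, and Section 8.1.2 says the pilot studies were meant to select a bioequivalent formulation. This also stands: a bias favouring one product is a possibility, not a finding.

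Last, the SAP might already deal with this. Section 12.2 allows that, but nothing in the supplied text does so.

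**Conclusion.** The point holds in a limited form. The linear rule across the unsampled 12 to 24 h interval can overstate AUC0-t and AUC0-inf for late-peaking or slowly eliminated profiles that are still measurable at 24 h. Under the assumed profiles the overstatement is about 5 to 23% for tmax up to 8 h, and about 20 to 50% at tmax 10 h. Typical profiles are essentially unaffected.

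The size for the trial as a whole cannot be settled from the documents. The LLOQ, the spread of tmax and half-life, and the share of profiles measurable at 24 h are not given. Section 8.1.1 says only that most individuals have no MMF left by then; it does not show that the rest would be quantifiable in this assay, and it concerns the reference product. A reader might infer that the bioequivalence conclusion is biased. The documents do not support that: the ratio or the CI width changes only if affected profiles differ between products or periods. This is a low-cost improvement to the definition of a decision parameter, not a defect that undermines the design.

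**What to change.** In Section 12.1 and the SAP, specify the linear-up/log-down trapezoidal method for AUC0-t, and hence AUC0-inf: linear while concentrations rise (and where a value is zero or two values are equal), logarithmic while they fall. Apply it to both products and fix it before data are seen. Report the AUC results under the linear rule as a sensitivity analysis.

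The cost is one phrase in each document and one setting in the noncompartmental software, with no extra samples. AUC values fall by about 0.5 to 1% for typical profiles in both products. They become slightly less comparable with any earlier results computed by the linear rule, which is a further reason to keep the linear result in the report.
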